4.5.3 Physical Examinations

A complete physical examination, performed at screening and other specified visits, should include an evaluation of the head, eyes, ears, nose, and throat and the cardiovascular, dermatologic, musculoskeletal, respiratory, gastrointestinal, genitourinary, and neurologic systems. Any abnormality identified at baseline should be recorded on the General Medical History and Baseline Conditions eCRF.

Limited, symptom-directed physical examinations should be performed at specified post-baseline visits and as clinically indicated. Changes from baseline abnormalities should be recorded in patient notes. New or worsened clinically significant abnormalities should be recorded as adverse events on the Adverse Event eCRF.

4.5.4 Vital Signs

Vital signs will include measurements of respiratory rate, pulse rate, systolic and diastolic blood pressure, and temperature. Record abnormalities observed at baseline on the General Medical History and Baseline Conditions eCRF. At subsequent visits, record new or worsened clinically significant abnormalities on the Adverse Event eCRF.

On study treatment days, vital signs will be measured within 60 minutes before the first study drug infusion of the day (see [Table 2](#)).

For the first infusion of atezolizumab, measure vital signs every 15 (± 5) minutes during the infusion and within 30 (± 10) minutes after the infusion. For the first infusion of tiragolumab/placebo, measure vital signs every 15 (± 5) minutes during the infusion and within 30 (± 10) minutes after the infusion. For subsequent administration of atezolizumab and/or tiragolumab/placebo, measure vital signs during each infusion only as clinically indicated and within 30 (± 10) minutes after the end of each infusion. Additional vital signs should be measured during the infusion if clinically indicated or if symptoms occurred in the prior infusion.

4.5.5 Performance Status

Performance status will be measured using ECOG Performance Status at baseline and will be assessed at regular intervals throughout the study (see Schedule of Activities in [Appendix 1](#)). For further details, see [Appendix 10](#).

4.5.6 Tumor and Response Evaluations

Screening and subsequent tumor assessments must include CT scans (with oral and/or IV contrast unless contraindicated). A CT scan of the pelvis is required at screening and as clinically indicated or as per local standard of care at subsequent response evaluations. MRI scans with contrast of the chest, abdomen, and pelvis with a non-contrast CT scan of the chest may be used in patients for whom CT scans with contrast are contraindicated (i.e., patients with contrast allergy or impaired renal clearance).

A CT (with contrast) or MRI scan with contrast (if CT contrast is contraindicated) of the head must be done at screening to evaluate CNS metastasis in all patients. If CT with contrast is performed and the presence of brain metastases is considered equivocal, an MRI scan of the brain is required to confirm or refute the diagnosis of CNS metastases at baseline.

Patients with active or untreated symptomatic CNS metastases are not eligible for the study (see Section 4.1.2). Patients with untreated asymptomatic CNS metastasis at screening may be eligible. For untreated patients, brain MRI scan with contrast at screening is required, and need to meet all eligibility criteria as specified in Section 4.1.2.

If a CT scan for tumor assessment is performed in a positron emission tomography (PET)/CT scanner, the CT acquisition must be consistent with the standards for a full contrast diagnostic CT scan.

Further investigations such as bone scans and CT scans of the neck should also be performed if clinically indicated. At the investigator's discretion, other methods of assessment of measurable disease as per RECIST v1.1 may be used.

Tumor assessments performed as standard of care prior to obtaining informed consent and within 28 days of Cycle 1, Day 1 may be used rather than repeating tests. All known sites of disease, including measurable and/or non-measurable disease, must be documented at screening and re-assessed at each subsequent tumor evaluation.

At subsequent (post-screening) tumor assessments, patients with a history of treated brain metastases at screening are not required to undergo brain scans unless clinically indicated (e.g., in patients with neurological symptoms). The same radiographic procedure used to assess disease sites at screening should be used throughout the study (e.g., the same contrast protocol for CT scans).

For patients with previously untreated CNS metastases, a brain MRI scan with contrast is required at screening and is the preferred modality for all subsequent scheduled follow-up tumor assessments.

Note: CT scan with contrast may be acceptable for all subsequent scheduled follow-up tumor assessments if the following criteria are met:

- Both brain MRI and CT scan with contrast must be performed at screening to assess untreated CNS disease, and
- The CT scan with contrast can be used to reliably evaluate lesions identified on the screening MRI with contrast. If CT scan with contrast cannot be used to reliably evaluate lesions identified on the screening MRI with contrast, then MRI scan with contrast must be used at all subsequent scheduled follow-up tumor assessments. The same modality must be used at every tumor assessment.

Untreated CNS disease must be recorded in the Tumor Assessment eCRF per RECIST v1.1 at screening as well as at subsequent scheduled follow-up tumor assessments.

Patients will undergo tumor assessments at baseline and at every 6 weeks (± 7 days) for 48 weeks following Day 1 of Cycle 1, regardless of treatment delays. After the completion of the Week 48 tumor assessment, tumor assessment will be required every 9 weeks (± 7 days) regardless of treatment delays, until radiographic disease progression per RECIST v1.1 (or loss of clinical benefit for patients who continue study treatment after disease progression per RECIST v1.1), withdrawal of consent, death, or study termination by the Sponsor, whichever occurs first (see Section 3.1.2). At the investigator's discretion, scans may be performed at any time if progressive disease or loss of clinical benefit is suspected. *After the CCOD (31 August 2023) of primary analysis, we will continue to follow ongoing patients under treatment in the study for limited information. Tumor assessments will no longer be required and investigators may continue to report tumor assessment results based on the frequency as per local practices to determine if patients have disease progression per RECIST v1.1.*

Response will be assessed by the investigator on the imaging modalities detailed above, using RECIST v1.1 (see Appendix 4). The investigator's assessment of overall tumor response at all timepoints should only be based on RECIST v1.1. Assessments should be performed by the same evaluator if possible to ensure internal consistency across visits. Results must be reviewed by the investigator before dosing at the next cycle.

Study treatment may be continued as long as patients are experiencing clinical benefit as assessed by the investigator in the absence of unacceptable toxicity or symptomatic deterioration attributed to disease progression after an integrated assessment of radiographic data, biopsy results (if available), and clinical status. Patients who meet criteria for disease progression per RECIST v1.1 will be permitted to continue study treatment if they meet all of the criteria specified in Section 3.1.2.

Patients who discontinue treatment for reasons other than radiographic disease progression per RECIST v1.1 (e.g., toxicity, symptomatic deterioration) will continue scheduled tumor assessments at the frequency described above until radiographic disease progression per RECIST v1.1, withdrawal of consent, death, or study termination by Sponsor, whichever occurs first.

After the CCOD (31 August 2023) of primary analysis, we will only continue to follow ongoing patients under treatment in the study for limited information, and tumor assessments are performed to determine if they have disease progression per RECIST v1.1. Tumor assessments will no longer be required for patients who discontinue treatment, no matter what the reasons are.

Patients who start a new anti-cancer therapy in the absence of radiographic disease progression per RECIST v1.1 will continue tumor assessments at the frequency described above until radiographic disease progression per RECIST v1.1, withdrawal of consent, death, or study termination by the Sponsor, whichever occurs first.

Investigator assessment of overall tumor response at all timepoints will be only based on RECIST v1.1. The Sponsor will derive the overall tumor assessment as per iRECIST based on entries for all target lesions, non-target lesions, and new lesions. To facilitate evaluation of response per iRECIST, tumor assessments must be continued after disease progression per RECIST v1.1 for patients who receive study treatment beyond progression. This includes continued measurement of target lesions, evaluation of non-target lesions (including monitoring for further worsening of any non-target lesions that have shown unequivocal progression), and evaluation of any newly identified lesions (including measurements, if lesions are measurable; see [Appendix 4](#)) at all subsequent assessments.

4.5.7 Laboratory, Biomarker, and Other Biological Samples

Samples for the following laboratory tests will be sent to the study site's local laboratory for analysis. Central laboratory analysis will be permitted only if local laboratory testing is not available.

- Hematology: WBC count with differential (neutrophils, eosinophils, basophils, monocytes, lymphocytes), RBC count, hemoglobin, hematocrit, platelet count, and differential count
- Chemistry panel (serum or plasma): bicarbonate or total carbon dioxide (if considered standard of care for the region), sodium, magnesium, potassium, calcium, chloride, glucose, BUN or urea, creatinine, total protein, albumin, phosphate, total bilirubin, ALP, ALT, AST, and LDH
- Coagulation: INR, and aPTT
- Thyroid function testing: thyroid-stimulating hormone, free triiodothyronine (T3) (or total T3 for sites where free T3 is not performed), and free thyroxine (also known as T4)

- HIV serology
- HBV serology: HBsAg, HBsAb, and total HBcAb for all patients; HBV DNA for patients with negative HBsAg and HBsAb tests and a positive total HBcAb
- HCV serology: HCV antibody and (if HCV antibody test is positive) HCV RNA
- EBV serology, including the following:
 - EBV VCA IgM
 - EBV PCR (if EBV VCA IgM test not available)
- Pregnancy test

All women of childbearing potential will have a serum pregnancy test at screening. During the study, urine pregnancy tests will be performed on Day 1 of every cycle, and after study treatment is discontinued (see [Appendix 1](#)). If a urine pregnancy test is positive, it must be confirmed by a serum pregnancy test.

- Urinalysis, including dipstick (pH, specific gravity, glucose, protein, ketones, blood)

The following samples will be sent to one or several central laboratories or to the Sponsor or a designee for analysis:

- Serum samples for tiragolumab and atezolizumab PK analysis through use of validated assays
- Serum samples for assessment of ADAs to tiragolumab through use of validated assays
- Serum samples for analysis of autoantibodies

Serum samples collected for the assessment of pharmacokinetics, ADAs, or biomarkers at baseline on Day 1 of Cycle 1 prior to the first dose of study treatment may be used for autoantibody testing if an immune-mediated adverse event develops in a patient that would warrant such an assessment.

- Pre-treatment tumor sample

A representative formalin-fixed paraffin-embedded (FFPE) pre-treatment tumor specimen in the format of slide (10 slides) containing unstained, freshly cut, serial sections should be submitted along with an associated pathology report for [REDACTED]

Patients may enroll into the study before submitting a pre-treatment tumor tissue sample. A pre-treatment tumor tissue (archival or freshly obtained) sample should be submitted within 4 weeks after randomization unless tissue sample collection is not permitted by HGRAC.

Preferred sample types include FFPE samples prepared from resections, core needle, excisional, incisional, punch, or forceps biopsies. If these sample types are not available, any type of specimen (including fine-needle aspiration, cell pellet specimens [e.g., from pleural effusion and lavage samples]) is acceptable.

Tumor tissue should be of good quality based on total and viable tumor content. Tumor tissue from bone metastases that is subject to decalcification is not advisable.

[REDACTED] Research may involve using *next-generation sequencing* methods from RNA isolated from the tissue. [REDACTED]
[REDACTED]

For sampling procedures, storage conditions, and shipment instructions, see the laboratory manual.

Biological samples will be destroyed no later than the time of completion of the final Clinical Study Report, with the following exceptions:

- Serum and plasma samples collected for PK or immunogenicity analysis may be needed for additional immunogenicity characterization and for PK or immunogenicity assay development and validation; therefore, these samples will be destroyed no later than 5 years after the final Clinical Study Report has been completed, or earlier depending on local regulations.
- Tumor tissue samples collected for exploratory biomarker research will be destroyed no later than 5 years after the final Clinical Study Report has been completed or earlier depending on local regulations. However, the storage period will be in accordance with the IRB/EC-approved Informed Consent Form and applicable laws (e.g., health authority requirements).

When a patient withdraws from the study, samples collected prior to the date of withdrawal may still be analyzed, unless the patient specifically requests that the samples be destroyed, or local laws require destruction of the samples. However, if samples have been tested prior to withdrawal, results from those tests will remain as part of the overall research data.

Data arising from sample analysis will be subject to the confidentiality standards described in Section 8.4.

Given the complexity and exploratory nature of exploratory biomarker analyses, data derived from these analyses will generally not be provided to study investigators or patients unless required by law. The aggregate results of any conducted research will be available in accordance with the effective Sponsor policy on study data publication.

4.5.8 Electrocardiograms

ECG is required at screening and as clinically indicated during the study. ECGs should be obtained on the same machine whenever possible. Lead placement should be as consistent as possible. ECG recordings should be performed after the patient has been resting in a supine position for at least 10 minutes.

For safety monitoring purposes, the investigator must review all ECG tracings. Copies of ECG tracings will be kept as part of the patient's permanent study file at the site. Any morphologic waveform changes or other ECG abnormalities must be documented on the eCRF.

4.5.9 Clinical Outcome Assessments

PRO data will be collected to document the treatment benefit and more fully characterize the clinical profile of tiragolumab plus atezolizumab. PRO data will be collected using the following instruments: EORTC QLQ-C30, single-item EORTC IL46, select items from the PRO-CTCAE, and the EQ-5D-5L. *PRO instrument completion is applicable through CCOD (31 August 2023) for the primary analysis.*

4.5.9.1 Data Collection Methods for Clinical Outcome Assessments

Paper versions of the PRO instruments will be self-administered during the treatment visits and interviewer administered by site personnel to the patient over the telephone during follow-up visits so that data can be collected without mandating patients' travel to the clinical site (see Schedule of Activities in [Appendix 1](#)). PRO data will be entered into the study database by the site personnel. The questionnaires will be translated into the local language as required. For patients who are unable to return to the clinic because of government restrictions or personal safety, PROs may be completed by means of a telephone call; source documentation should be obtained that includes, among other information, the questionnaires administered via telephone.

To ensure instrument validity and that data standards meet health authority requirements, questionnaires scheduled for administration during a clinic visit will be completed in their entirety by the patient prior to receiving any information on disease status, prior to the performance of non-PRO assessments that could bias patients' answers, and prior to the administration of study treatment, unless otherwise specified.

PROs should be administered as outlined below:

- Patients' health status should not be discussed prior to administration of the instruments.
- Sites must administer the official version of each instrument, as provided by the Sponsor. Instruments must not be copied from the protocol.
- Sites should allow sufficient time for patients to complete the instruments.
- Sites should administer the instruments in a quiet area with minimal distractions and disruptions.

- Patients should be instructed to answer questions to the best of their ability; there are no right or wrong answers.
- Site staff should not interpret or explain questions but may read questions verbatim upon request.
- Patients should not obtain advice or help from others (e.g., family members or friends) when completing the instruments.
- Site staff should review all completed instruments and should ask the patient to rectify any response that is not clearly marked in the appropriate location. If a response is missing, site staff should ask the patient to complete the item or confirm that the item was intentionally left blank.

The questionnaires (EORTC QLQ-C30, EORTC IL46, PRO-CTCAE [select items], and EQ-5D-5L) will be completed during the induction phase at Cycle 1, Day 1 (baseline) prior to administration of study drug; then at every study treatment cycle prior to administration of study drug (i.e., on Cycle 2, Day 1; Cycle 3, Day 1; and Cycle 4, Day 1).

Starting at Cycle 5, the questionnaires will be completed at every other study treatment cycle prior to administration of study drug (i.e., on Cycle 5, Day 1; Cycle 7, Day 1; Cycle 9, Day 1; and so forth), and at the study treatment discontinuation visit (see [Appendix 1](#)).

Patients who discontinue study treatment for any reason other than radiographic disease progression per RECIST v1.1 (e.g., toxicity, symptomatic deterioration) will complete the EORTC QLQ-C30, PRO-CTCAE (select items), and EQ-5D-5L at each tumor assessment visit until radiographic disease progression per RECIST v1.1, death, loss to follow-up, consent withdrawal, or study termination by the Sponsor, whichever occurs first. Patients who continue to receive treatment after the confirmation of disease progression per RECIST v1.1 will complete the questionnaires at every other study treatment cycle until study treatment discontinuation.

During survival follow-up, for patients with radiographic disease progression per RECIST v1.1, the PRO questionnaires will be completed at 3 months (\pm 30 days) and 6 months (\pm 30 days) following the visit in which progressive disease was confirmed. For patients who continued treatment after disease progression per RECIST v1.1, PRO questionnaires will be completed at 3 months [\pm 30 days] and 6 months [\pm 30 days] following the study treatment discontinuation visit.

Patients whose native language is not available with the questionnaires are exempted from completing all PRO assessments.

The Sponsor will not derive adverse events reports from PRO data.

4.5.9.2 Description of Clinical Outcome Assessment Instruments

EORTC QLQ-C30

The EORTC QLQ-C30 is a validated, reliable self-reported measure (Aaronson et al. 1993; Fitzsimmons et al. 1999) (see [Appendix 6](#)). It consists of 30 questions that assess five aspects of patient functioning (physical, emotional, role, cognitive, and social), three symptom scales (fatigue, nausea and vomiting, and pain), GHS and QoL, and six single items (dyspnea, insomnia, appetite loss, constipation, diarrhea, and financial difficulties) with a recall period of the previous week. Scale scores can be obtained for the multi-item scales. The functioning and symptoms items are scored on a 4-point scale that ranges from "not at all" to "very much," and the GHS and QoL items are scored on a 7-point scale that ranges from "very poor" to "excellent." The EORTC QLQ-C30 module takes approximately 15 minutes to complete.

EORTC IL46

EORTC IL46 is a validated single-item question assesses overall side-effect impact ([Appendix 7](#)).

PRO-CTCAE

The PRO-CTCAE is a validated item bank that is used to characterize presence, frequency, severity, and interference with daily function of 78 patient-reportable symptomatic treatment toxicities (Basch et al. 2014; Dueck et al. 2015).

The PRO-CTCAE contains 124 questions that are rated on either a 5-point Likert scale (frequency, severity and interference) or dichotomously (presence/absence).

Included treatment toxicity terms can be subjective, with or without observable components (e.g., vomiting and nausea, respectively), or primarily observable with subjective components (e.g., rash). The standard PRO-CTCAE recall period is "the past 7 days." A subset of three symptoms that were deemed most applicable to the current treatments were selected for this study ([Appendix 8](#)).

EQ-5D-5L

The EQ-5D-5L is a validated self-report health status questionnaire that is used to calculate a health status utility score for use in health economic analyses (EuroQol Group 1990; Brooks 1996; Herdman et al. 2011; Janssen et al. 2013) (see [Appendix 9](#)). There are two components to the EQ-5D-5L: a five-item health state profile that assesses mobility, self-care, usual activities, pain/discomfort, and anxiety/depression, as well as a visual analogue scale that measures health state. The EQ-5D-5L is designed to capture the patient's current health status. Published weighting systems allow for creation of a single composite score of the patient's health status. The EQ-5D-5L takes approximately 3 minutes to complete. It will be used in this study for informing pharmacoeconomic evaluations.

4.6 PATIENT, TREATMENT, STUDY, AND SITE DISCONTINUATION

4.6.1 Study Treatment Discontinuation

Patients must discontinue study treatment if they experience any of the following:

- Symptomatic deterioration attributed to disease progression as determined by the investigator after integrated assessment of radiographic data, biopsy results if available, and the patient's clinical status
- Intolerable toxicity related to study treatment, including development of an immune-mediated adverse event determined by the investigator to be unacceptable given the individual patient's potential response to therapy and severity of the event
- Any medical condition that may jeopardize the patient's safety if he or she continues on study treatment
- Use of another non-protocol-specified anti-cancer therapy (NPT) (see Section 4.4.3)
- Pregnancy
- Radiographic disease progression per RECIST v1.1 (unless treating beyond radiographic progression; see below)

However, to better accommodate standard clinical practice which is guided by the fact that patients with ES-SCLC whose disease progresses after 1L treatment have limited treatment options and such options also have limited efficacy and significant toxicity, patients may be considered for treatment beyond radiographic progression per RECIST v1.1 at the discretion of the investigator and after appropriate discussion with the patient, only if all of the following criteria are met:

- Evidence of clinical benefit as assessed by the investigator
- No decline in ECOG Performance Status that can be attributed to disease progression
- Absence of tumor progression at critical anatomical sites (e.g., leptomeningeal disease) that cannot be managed by protocol-allowed medical interventions

Treatment should be discontinued if patients experience any of the following:

- Loss of clinical benefit (if treatment with tiragolumab or placebo and atezolizumab) or clinical deterioration due to disease progression occurs at any time or if persistent disease growth is confirmed as determined by investigator after an integrated assessment of radiographic and biochemical data, clinical status, and local biopsy results (if available)
- Unacceptable toxicity

The primary reason for study treatment discontinuation should be documented on the appropriate eCRF. Patients who discontinue study treatment prematurely will not be replaced.

Patients will return to the clinic for a treatment discontinuation visit \leq 30 days after the final dose of study treatment (see [Appendix 1](#)). The visit at which response assessment shows progressive disease may be used as the treatment discontinuation visit. Patients who discontinue study treatment for any reason other than progressive disease or loss of clinical benefit will continue to undergo tumor response assessments and PRO assessments as outlined in the Schedule of Activities (see [Appendix 1](#)). *PRO instrument completion is applicable through CCOD (31 August 2023) for the primary analysis.*

After treatment discontinuation, information on survival follow-up and new anti-cancer therapy will be collected via telephone calls, patient medical records, and/or clinic visits approximately every 3 months until death (unless the patient withdraws consent or the Sponsor terminates the study) (see [Appendix 1](#)). Information on subsequent anti-cancer therapies will include systemic therapies (e.g., chemotherapy, targeted therapy, hormonal therapy, or cancer immune therapy), surgery (e.g., resection of metastatic disease), and radiation procedures (e.g., radiotherapy to a tumor lesion). *Follow-up activities completion is applicable through CCOD (31 August 2023) for the primary analysis.*

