Following the induction phase, patients will continue maintenance therapy with either tiragolumab plus atezolizumab (Arm A) or placebo plus atezolizumab (Arm B). During the maintenance phase, prophylactic cranial irradiation (PCI) is permitted (though not mandated) per local standard of care and will be reported on the Prophylactic Cranial Irradiation Electronic Case Report Form (eCRF). Consolidative thoracic radiation with curative intent or the intent to eliminate residual disease is not permitted. Palliative radiation for symptomatic management is allowed (please refer to Section [4.4.1](#) for further details).

Treatment will be continued until radiographic disease progression according to RECIST v1.1, or as long as patients are experiencing clinical benefit, as assessed by the investigator, in the absence of unacceptable toxicity or symptomatic deterioration attributed to disease progression after an integrated assessment of radiographic data, biopsy results (if available), and clinical status. Patients who meet the criteria for

disease progression per RECIST v1.1 will be permitted to continue study treatment (tiragolumab plus atezolizumab or placebo plus atezolizumab) if they meet all of the criteria specified in Section [3.1.2](#) and provide written consent.

A safety review of unblinded data will be performed by an independent Data Monitoring Committee (iDMC; see Section [3.1.3](#)) after approximately 6 months from the time of randomization of the first patient until the study data are unblinded or the study is terminated by the Sponsor.

Patients will undergo tumor assessments at baseline and every 6 weeks (± 7 days) for 48 weeks following Cycle 1, Day 1, regardless of treatment dose delays.

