3.1.2 Treatment after Disease Progression

During the study, patients who meet criteria for disease progression per RECIST v1.1 and show evidence of clinical benefit may continue treatment at the investigator's discretion, provided that the patients meet all of the following criteria:

- Evidence of clinical benefit, as assessed by the investigator
- Absence of symptoms and signs (including worsening of laboratory values [e.g., new or worsening hypercalcemia]) indicating unequivocal progression of disease
- No decline in ECOG Performance Status that can be attributed to disease progression
- Absence of tumor progression at critical anatomical sites (e.g., leptomeningeal disease) that cannot be managed by protocol-allowed medical interventions
- The patient has been informed that continuing study treatment may result in further progression and delay treatment with subsequent therapies for which they are eligible and has signed the Optional Treatment Beyond Initial Radiographic Progression Informed Consent Form

Investigator assessment of overall tumor response at all timepoints will be based only on RECIST v1.1. Objective response per iRECIST will be calculated programmatically by the Sponsor on the basis of investigator assessments of individual lesions at each specified timepoint.

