Patients with ES-SCLC experience rapid tumor growth and fast clinical deterioration and have an overall poor prognosis. First-line therapy with atezolizumab plus CE has demonstrated high response rates and significant clinical benefit. However, after disease progression, treatment options are limited, and such options have shown limited efficacy and significant toxicity (see Section 1.2). Given that the greatest opportunity to achieve a clinically significant benefit from therapy is in the front-line setting and given the poor efficacy and high toxicity profile of second-line therapies, patients may be considered for treatment beyond radiographic disease progression per RECIST v1.1 at the discretion of the investigator and after appropriate discussion with the patient, only if they meet all of the criteria described in Section 3.1.2.

In addition, conventional response criteria may not adequately assess the activity of immunotherapeutic agents because progressive disease (by initial radiographic evaluation) does not necessarily reflect therapeutic failure. Because of the potential for pseudoprogression/tumor-immune infiltration, this study will allow patients to remain on treatment after apparent radiographic disease progression per RECIST v1.1, provided all criteria in Section 3.1.2 are met. Treatment should be discontinued if clinical

deterioration due to disease progression occurs at any time or if persistent disease growth is confirmed in a follow-up scan. In addition, patients should be discontinued for unacceptable toxicity or for any other signs or symptoms of deterioration attributed to disease progression as determined by the investigator after an integrated assessment of radiographic data and clinical status (see Section 4.6.1).

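### Does the shorter list in Protocol Section 4.6.1 loosen the conditions for treatment beyond RECIST v1.1 progression?

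*Protocol*

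**What the plan says.** Section 4.6.1 lists the events at which study treatment must stop. One is "Radiographic disease progression per RECIST v1.1 (unless treating beyond radiographic progression; see below"), and the text that follows lets the investigator consider continuing "at the discretion of the investigator and after appropriate discussion with the patient, only if all of the following criteria are met". Three criteria come next: clinical benefit in the investigator's view, no fall in ECOG performance status due to progression, and no progression at a critical site that allowed interventions cannot manage.

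Section 3.1.2 has those three and two more. One is "Absence of symptoms and signs (including worsening of laboratory values [e.g., new or worsening hypercalcemia]) indicating unequivocal progression of disease". The other is that the patient has been told of the risks of continuing and "has signed the Optional Treatment Beyond Initial Radiographic Progression Informed Consent Form".

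Other sections send the reader to 3.1.2. Section 3.1.1 says that patients with RECIST v1.1 progression "will be permitted to continue study treatment (tiragolumab plus atezolizumab or placebo plus atezolizumab) if they meet all of the criteria specified in Section" (the section it names is 3.1.2), and it asks for written consent as well. Section 3.4.5 uses almost the same sentence as 4.6.1 but ends it differently: "after appropriate discussion with the patient, only if they meet all of the criteria described in Section 3.1.2".

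**The concern.** Section 4.6.1 is operative text. Sections 4.3.2.3 and 4.3.2.4 name it, with 5.1.6, as the place for guidance on interrupting or stopping treatment. It introduces its three criteria as all that must be met, its exception points only to the text below it, and it never mentions 3.1.2. A site working from that section alone could conclude that three conditions suffice. It might then continue a patient whose signs or laboratory values 3.1.2 would treat as disqualifying, or dose the patient after a conversation but without the separate consent form.

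The consent section does not repair the trail. Section 4.5.1 requires written consent before dosing beyond progression, but it cites Section 4.3.4, which deals with access to drug through an extension study. At stake would be uniform stopping decisions across sites and valid consent for continued dosing.

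**Working it through.** No statistical figure is involved, so the check is a comparison of the texts.

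**Step 1: match the criteria.**

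| Condition for continuing after RECIST v1.1 progression | 3.1.2 | List in 4.6.1 |
|---|---|---|
| Clinical benefit | yes | yes |
| No symptoms, signs or laboratory worsening showing unequivocal progression | yes | no |
| No ECOG decline due to progression | yes | yes |
| No unmanageable progression at a critical site | yes | yes |
| Patient informed and consent form signed | yes | no |

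Section 3.1.2 has 5 criteria and 4.6.1 has 3, so 5 − 3 = 2 are not repeated. Nothing in 4.6.1 is absent from 3.1.2.

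**Step 2: do the lists conflict?** They would if meeting one broke the other. Because the three are a subset of the five, any patient who meets 3.1.2 also meets 4.6.1. The wording of 4.6.1 is also restrictive: patients may be considered only if the three hold. That makes the three necessary; it does not say that they are enough.

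**Step 3: which conditions does the whole plan impose?** Protocol 3.1.1, 3.4.5 and 4.5.6 and SAP 1.2 each require all the criteria of 3.1.2, which makes four sections. Appendix 5 also refers decisions on continuing beyond progression to 3.1.2. Section 4.5.6 matters most in practice, because it governs the tumour assessment at which progression is found.

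**Step 4: is the symptoms-and-signs criterion covered elsewhere?** Section 4.6.1 has three stop rules that bear on it:
- symptomatic deterioration attributed to progression;
- loss of clinical benefit, clinical deterioration due to progression, or a finding that "persistent disease growth is confirmed as determined by investigator after an integrated assessment of radiographic and biochemical data, clinical status", which brings laboratory data into the judgement;
- "Any medical condition that may jeopardize the patient's safety if he or she continues on study treatment".

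Section 3.4.5 adds that patients should stop for other signs or symptoms of deterioration put down to progression, and it cites 4.6.1 when it says so.

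**Step 5: is consent covered elsewhere?** Written consent for continuing is required in Protocol 3.1.1, 3.1.2 and 4.5.1 and in SAP 1.2, four places in all. Section 4.5.1 is the informed-consent section and states the rule in full; only its cross-reference is wrong.

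**Step 6: does it reach an endpoint?** PFS runs to the first RECIST v1.1 progression or death (Protocol 6.4.1, SAP 5.3.1.1), so treatment beyond progression starts after the PFS event. OS counts death from any cause, with a treatment policy for early discontinuation and for new anti-cancer therapy (SAP 5.3.1.2). Neither definition depends on which list a site reads.

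**The case for a change.** The strongest case for a change is that a stopping rule should be complete where sites are told to look for it. The stop rules in 4.6.1 are also not the same thing as the missing criterion. Section 3.1.2 sets a condition for continuing at all, whereas 4.6.1 uses biochemical data only as one input to an overall judgement. A discussion with the patient is not a signed form. Section 3.4.5 is a rationale section and carries less weight as an instruction. The rule is also still live, because patients on treatment continue after the 31 August 2023 cutoff.

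Much of this stands as a description. The list in 4.6.1 is incomplete, and the reference in 4.5.1 is wrong. The practical consequence is what does not follow. For the gap to matter, a patient would need signs or laboratory changes that show unequivocal progression while the investigator still found clinical benefit, no clinical deterioration, no ECOG decline due to progression and no safety concern. Those findings hardly fit together. For consent to be missed, site staff would have to overlook the consent section as well as 3.1.1 and 3.1.2. Both cases assume that one section is read in isolation from a protocol that repeatedly directs the reader to 3.1.2.

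**Conclusion.** No change to the plan is called for. Section 4.6.1 restates three of five criteria and leaves out a cross-reference, and Section 4.5.1 cites the wrong section. Both are clerical slips. The two lists are compatible, the plan read as a whole already requires all five criteria and written consent, and neither co-primary endpoint definition is touched.

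This rests on two assumptions: that sites apply the protocol as a whole, and that 4.6.1 is read as setting necessary conditions. The documents do not say how many patients were treated beyond progression, so the number who could be affected cannot be stated. After the cutoff it is limited to those still on treatment. If the protocol is reopened for another reason, the two sections could be aligned as housekeeping. A bare cross-reference would still leave two lists standing, and the content of a single list is for the sponsor's clinical team to settle.
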